5.2 Safety Analysis Set (SAF)

For the statistical summary of the safety data, the SAF will be used.

[Phase 1 part]

All subjects who received at least 1 dose of study drug will be included.

[Phase 2 part]

The SAF will be defined as the same as Phase 1 part.

5.3 Dose-Determining Analysis Set (DDAS)

[Phase 1 part]

Subjects who do not fall under any of the following criteria will be included:

- Received less than 80% of the intended dose of ASP2215 during DLT assessment period specified in each part (e.g., subject in dose evaluation part who misses ≥ 3 daily doses during DLT assessment period and interrupts the study for a reason other than a DLT)
- Unable to assess safety adequately during DLT assessment period specified in each part such as due to the lack of required safety assessment(s).

[Phase 2 part]

Not applicable.

5.4 Pharmacokinetics Analysis Set (PKAS)

Subjects who received the study drug, from whom samples for drug concentration measurement have been collected for at least 1 time-point after the study drug administration, and from whom drug concentration measurement has been obtained will be included.

5.5 Pharmacodynamic Analysis Set (PDAS)

[Phase 1 part]

Subjects who received the study drug, from whom samples for pharmacodynamic assessment have been collected for at least 1-time point after the study drug administration, and from whom pharmacodynamic measurement has been obtained will be included.

[Phase 2 part]

Not applicable.

5.6 MRD Analysis Set (MAS)

[Phase 1 part]

Not applicable.

[Phase 2 part]

Subjects who received at least one dose of study drug, were centrally confirmed as FLT3-ITD positive at screening and had a baseline and at least one post-baseline sample with MRD data.

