Defined as the time from the date of start date of the treatment until the date of having a neutrophil count of $\geq 1,000/\text{mm}^3$ and platelet count of $\geq 100,000/\text{mm}^3$. Subjects with none of these events are censored at the date of last assessment within each treatment cycle.

- MRD

MRD is defined as binary endpoint, negative or positive. More detail of the definition is in Section 6.5. MRD rate is defined as the percentage of subjects whose MRD is negative.

- MR

MR is defined as binary endpoint, MR or no MR. More detail of the definition is in Section 6.5. MR rate is defined as the percentage of subjects who achieve MR.

- MRD-negative CR rate after induction

Defined as the number of subjects who achieve the best response of CR and whose MRD is negative during induction period divided by the number of subjects in the analysis population during induction therapy period. Subjects with unknown or missing response, or who provide no information on response will be treated as non-responders and will be included in the denominator when calculating rates.

- Overall MRD-negative CR rate for any treatment period

Defined as the number of subjects who achieve the best response of CR and at least one post-baseline MRD is negative divided by the number of subjects in the analysis population. If subjects have multiple MRD samples collected across different timepoints, the overall MRD status is negative if there is at least one MRD sample is negative and the overall MRD status is positive if all available MRD samples are positive. Subjects with unknown or missing post-baseline MRD status, or who provide no information on post-baseline MRD status will be treated as MRD positive and will be included in the denominator when calculating rates.

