6.5 Other Variables

- FLT3-ITD mutation status
- FLT3-TKD mutation status
- FLT3 mutation status

Either of FLT3-ITD mutation status or FLT3-TKD mutation status is positive, this variable shows positive.

- MRD

MRD negative is defined as summed FLT3-ITD signal ratio of any post-baseline sample $\leq 10^{-4}$. MRD positive is defined as summed FLT3-ITD signal ratio of any post-baseline sample $> 10^{-4}$.

- MR
MR is defined as summed FLT3-ITD signal ratio of any post-baseline sample $\leq 10^{-2}$.
No MR is defined as summed FLT3-ITD signal ratio of any post-baseline sample $> 10^{-2}$.
- FLT3-ITD signal ratio
FLT3-ITD signal ratio is defined as the ratio of FLT3-ITD sequence reads divided by the total number of FLT3 sequence reads. This is being calculated by central laboratory. For subjects with more than one FLT3-ITD variant, the FLT3-ITD signal ratio will be summed at each timepoint.
- Duration of exposure (days)
Duration of exposure to each treatment will be calculated in days, using the following formula:
 - Duration of exposure for each treatment cycle is defined as Last dose date – First dose date + 1 – (on-study HSCT period for subjects undergo on-study HSCT) for each cycle. For Phase1 part, last dose date of study drug exposure = (initial dose date of the cycle + 14 – 1) if last dose date of the cycle is not captured on dosing CRF.
 - Duration of exposure for each treatment period is calculated as sum of the duration of exposure for each treatment cycle.
 - Duration of exposure during study for study drug =
(Duration of exposure for Induction period) + (Duration of exposure for Consolidation period) + (Duration of exposure for Maintenance period).When the last date of exposure is beyond cutoff date, the cutoff date will be used as the last date of exposure. When the start or stop date is missing, then the exposure will be treated as missing.
- Number of dosing days (days)
Defined as number of days with non-zero dosing.
Number of dosing days is calculated for each treatment period.
- Cumulative dose (mg or g)
Defined as total amount of drug given to a patient, which calculated as follows:
 - ASP2215: Sum of (actual dose level * number of dosing days within each dose level)
 - Chemotherapy: Sum of actual dose across the days when administered.
Actual dose is calculated as:
(Actual volume administered / Total volume prepared)* Intended dose * Body surface area.

If number of doses taken is unknown, it will be treated as missing.

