7.4 Analysis of Efficacy

[Phase 1 part]

The efficacy analysis will be performed on the FAS.

For response variables, best response after each treatment therapy period will be summarized. The number and percentage of subjects in each category will be presented together with two-sided exact 95% CIs based on binomial distribution. Swimmer's plot will be presented for response variables.

For time-to-event variables efficacy analysis will be summarized using descriptive statistics. The survival curve and the median will be estimated using the Kaplan-Meier method and will be reported along with the corresponding 95% CIs.

[Phase 2 part]

The efficacy analysis will be performed on the FAS and TTE-FAS. The interpretation of statistical results will be based on the FAS. The TTE-FAS will be used to analyze OS and EFS. Analysis of MRD and MR will be performed using MAS.

Primary efficacy variable

For primary efficacy variable, CR rate after induction therapy period, the two-sided 90% exact CI by Clopper-Pearson method will be calculated. The lower limit will be used to compare with the benchmark of CR rate of 55%. The number and percentage of subjects in each category and swimmer's plot will also be presented. As a supportive analysis, CR rate after induction therapy period reported by Day 60 and CR rate after induction therapy period not being dependent on RBC and platelet transfusion (No Transfusion of RBC and Platelet within 1 week prior to disease assessment) will also be calculated.

Other efficacy variables

For other efficacy variables, analysis method will be described as follows:

Categorical variables:

The number and percentage of subjects in each category will be presented together with two-sided exact 95% CIs based on binomial distribution. Swimmer's plot will be presented for response variables.

For response assessment variables, best response rate after each treatment therapy will be summarized. The number and percentage of subjects in each category will be presented together with two-sided exact 95% CIs based on binomial distribution. For subjects who undergo HSCT, any response assessment data after HSCT will not be used (i.e. for those subjects, only response assessment data before HSCT will be used).

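### Neither analysis set that could apply to the MRD-based remission rates works with the SAP's own rules, and most MRD rates have no rule for samples that disagree across visits

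*SAP*

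**What the plan says.** **Sets.** Section 5.6 limits the MAS to treated subjects centrally confirmed FLT3-ITD positive at screening who "had a baseline and at least one post-baseline sample with MRD data". Section 7.4 (Phase 2) places efficacy on the FAS and TTE-FAS and states "The interpretation of statistical results will be based on the FAS". It then adds "Analysis of MRD and MR will be performed using MAS".

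**Rates.** Section 6.1.4 lists MRD and MR as endpoints in their own right. It lists separately an MRD-negative CR rate after induction and an Overall MRD-negative CR rate. Section 6.1.3 has CR and CRc rates without MRD after each therapy, modelled on the CR rate. All these remission rates are divided by an analysis population that is not named.

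**Missing MRD.** For the Overall rate, section 6.1.4 says that subjects with missing post-baseline MRD, or "who provide no information on post-baseline MRD status will be treated as MRD positive and will be included in the denominator when calculating rates".

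**Classes.** Section 6.5 says "MRD negative is defined as summed FLT3-ITD signal ratio of any post-baseline sample" at or below 10^-4, and "MRD positive is defined as summed FLT3-ITD signal ratio of any post-baseline sample" above 10^-4. MR and no MR follow the same pattern at 10^-2 ("No MR is defined as summed FLT3-ITD signal ratio of any post-baseline sample" above that value). The underlying quantity is specific to ITD: "FLT3-ITD signal ratio is defined as the ratio of FLT3-ITD sequence reads divided by the total number of FLT3 sequence reads".

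**Several samples.** For the Overall rate, one negative sample makes the subject negative, and a subject is positive only if every available sample is. For Phase 2 central-laboratory data, section 7.11.5 settles multiple observations at one visit: closest to target, then the later one; on the same day, the average or the worst value.

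**The concern.** The SAP has a conservative rule for missing MRD, but the set that it names for MRD analysis contains nobody to whom that rule could apply. The other candidate set lets the rule work but includes subjects whom the assay cannot classify. The choice is unwritten, so in an open-label, single-arm study the denominator could be settled after results are known. The same holds for a subject whose samples fall on both sides of a cut-off at different visits. At stake is the meaning of a group of secondary and exploratory rates: a rate among all eligible treated subjects, a rate among those with MRD results, or a rate mixed with unmeasurable subjects.

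**Working it through.** The SAP gives no figure for any MRD-based rate, so there is none to reproduce. Its one power statement (section 4.1.2) concerns the primary CR rate and is untouched: with 70 subjects the exact test succeeds at 46 responses, with power 82.0%, in line with the stated figure of more than 80%.

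**1. MAS against the missing rule.** Give each subject a result of negative, positive or missing in each of three periods (induction, consolidation, maintenance): 3^3 = 27 patterns.
- At least one post-baseline result, as the MAS requires: 26.
- Of these, overall post-baseline MRD missing: 0. On the MAS the rule acts on nobody.
- Of these, induction result missing but a later one present: 8. The void therefore concerns the Overall rate only; a missing-data rule for induction would still have subjects to act on.

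**2. FAS against the assay.** Section 6.5 calls a subject FLT3-mutated if ITD or TKD is positive, and section 7.8 lists TKD-positive as a category apart from both-positive. TKD-only subjects can therefore be in the FAS. If they are not assayed, the Overall rate counts them as MRD positive. If they are assayed, a ratio near 0 meets the negative cut-off. Neither result describes their residual disease, and the SAP does not say which applies.

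**3. Discordant samples.** Of the 26 patterns, 12 contain both a negative and a positive result. Read at subject level, section 6.5 puts those in both classes. Read per sample, there is no overlap, but a subject-level rule is then needed, because the MRD rate is a percentage of subjects. Coverage in the SAP is:

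| Situation | Rule |
|---|---|
| Several observations at one visit | section 7.11.5 |
| Across visits, Overall rate | section 6.1.4 |
| Across visits, MRD and MR rates | none |
| Across visits, induction rate | none |
| Across visits, CR/CRc without MRD | none |

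The 12 patterns show disagreement between periods. They do not show how often samples disagree within one period.

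**4. Illustration; every input is assumed.**
- r = 0.40, the rate among all treated FLT3-ITD positive subjects.
- m = share of them with no post-baseline MRD, none a responder.
- b = share who are responders but lack a baseline MRD sample.
- t = share of the FAS that is TKD-only; all subjects are taken to have a marrow assessment.
- TKD-only CR rate 55% or 70%, borrowed from the benchmark and target in section 4.1.2.

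MAS rate = (r − b)/(1 − m − b):

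| m | b | MAS rate |
|---|---|---|
| 0.05 | 0 | 0.40/0.95 = 42.1% |
| 0.10 | 0 | 0.40/0.90 = 44.4% |
| 0.20 | 0 | 0.40/0.80 = 50.0% |
| 0 | 0.05 | 0.35/0.95 = 36.8% |
| 0.10 | 0.05 | 0.35/0.85 = 41.2% |

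The shift is zero when b = rm/(1 − r); for m = 0.10 that is 0.04/0.60 = 0.067. Its sign is therefore not fixed.

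FAS rate with t = 0.20:
- not assayed: 0.40 × 0.80 = 32%;
- assayed and read as negative: 0.32 + 0.20 × 0.55 = 43%, or 0.32 + 0.20 × 0.70 = 46%.

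For t from 0.10 to 0.30 these become 36% to 28% not assayed, and 41.5% to 49% assayed.

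Reclassifying one CR subject moves a rate by 1/70 = 1.4 points to 1/50 = 2.0 points, for assumed denominators of 70 and 50.

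**The case against.** The best reply on the set is that section 7.4 sends only MRD and MR to the MAS. Section 6.1.4 lists those as endpoints separate from the MRD-negative CR rates, so the composite rates default to the FAS, where the missing rule works. That reading is fair, and the rule itself supports it. It means a reader should not conclude that the SAP assigns these rates to the MAS or that they will be inflated; the void rule is conditional on that reading. But the FAS reading brings in the TKD-only subjects, so the default does not rescue the rates. How many there are, and whether they are assayed, may be laid down outside the SAP.

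On discordance, *any post-baseline sample* reads naturally as any given sample, with complementary cut-offs. A reader might infer that section 6.5 flatly contradicts itself; that follows only from the subject-level reading. Section 7.11.5 also deals with repeats at one visit. And the SAP does not show that a subject has more than one MRD sample within a treatment period, so the induction and after-each-therapy rates may meet the problem rarely. What remains is that a subject-level percentage needs a rule across visits, and only the Overall rate has one.

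Finally, missing MRD in the induction and CR/CRc-without-MRD rates already fails the responder definition, which requires a negative result. That stands: for those rates the fix only makes the handling explicit.

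**Conclusion.** The point holds as a mismatch between analysis set and rule. If the MAS covers the Overall MRD-negative CR rate, the missing-counts-as-positive rule has no effect and the figure is a rate among subjects with MRD results. If the FAS applies, the denominator includes subjects whom an FLT3-ITD ratio cannot classify. Separately, no rule across visits is given for the MRD and MR rates, the induction rate, or the CR/CRc rates without MRD.

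Neither size nor direction can be determined from the SAP; the percentages above show only that unstated choices could move a reported rate by several points either way. The effect is confined to secondary and exploratory rates reported with descriptive confidence intervals. The primary CR rate, its benchmark comparison and its power are unaffected. This should be repaired, but it does not threaten the trial's main conclusion.

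**What to change.** - For the Overall, induction and CR/CRc-without-MRD rates, name as denominator all treated subjects centrally confirmed FLT3-ITD positive at screening (the TTE-FAS restricted to that group). Count missing MRD in the reported period as not negative.
- Keep the MAS for descriptive summaries of MRD and MR.
- State in section 6.5 that the 10^-4 and 10^-2 cut-offs classify each sample.
- Give one subject-level rule across visits for each reported period, for example the Overall rate's rule that one negative sample suffices, with a matching rule for MR.

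Naming the MAS alone would leave the missing rule without effect, and naming the FAS alone would leave TKD-only subjects unresolved. The cost is SAP wording and programming, with no additional samples, since missing results have a defined class. The drawback is that reported rates may be lower than on the MAS.

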6 ANALYSIS VARIABLES

6.1 Efficacy Endpoints

6.1.1 Response Definition

Antitumor response will be assessed on the days of bone marrow sampling based on the bone marrow findings, and peripheral blast count, neutrophil count, and platelet count. Preferably, samples from both bone marrow aspiration and biopsy should be obtained, but if the bone marrow aspiration was determined to be sufficient, biopsy may be omitted.

Antitumor response is defined per modified Cheson criteria (2003) or modified ELN recommendations (2017) as outlined below [Döhner et al, 2017; Cheson et al, 2003].

[Phase 1 part]

The assessment will be performed by the investigator. The results of bone marrow findings and peripheral blast count will be entered into the eCRF.

[Phase 2 part]

Bone marrow aspiration and/or biopsy samples and hematology samples are evaluated both centrally and locally. If bone marrow samples were obtained for unscheduled visits, those samples along with hematology samples should be submitted for central assessment.

Definitions

Complete Remission (CR):

CR is defined as a morphologically leukemia-free state at the post-baseline visit, having a neutrophil count of $\geq 1,000/\text{mm}^3$ and platelet count of $\geq 100,000/\text{mm}^3$, bone marrow myeloblasts $< 5\%$. There must be no evidence of Auer rods and no evidence of extramedullary leukemia. The blast counts in peripheral blood must be $\leq 2\%$.

Complete Remission with Partial Hematologic Recovery (CRh):

CRh is defined as a condition at the post baseline visit, having bone marrow myeloblasts $< 5\%$, partial hematologic recovery neutrophil count $\geq 500/\text{mm}^3$ and platelet count $\geq 50,000/\text{mm}^3$, no evidence of extramedullary leukemia and cannot be classified as CR. The blast counts in peripheral blood must be $\leq 2\%$.

Complete Remission with Incomplete Platelet Recovery (CRp):

CRp is defined as a condition that meets all of the CR criteria at the post-baseline visit, except for the unrecovered platelet count ($< 100,000/\text{mm}^3$).

Complete Remission with Incomplete Hematological Recovery (CRi):

CRi is defined as a condition that meets all of the CR criteria at the post-baseline visit, except for the unrecovered neutrophil count ($< 1,000/\text{mm}^3$) whether or not having unrecovered platelet counts).

Partial Remission (PR):

At a post-baseline visit, PR is defined as a condition with regeneration of normal hematopoietic cells in the bone marrow.

If bone marrow myeloblasts between 5% and 25% and a decrease from baseline of at least 50% in the marrow myeloblasts, no detectable (or trace of residual) blasts, and no evidence of extramedullary leukemia, the response is classified as PR.

Not Evaluable (NE)/No Response (NR):

In the situation where no bone marrow assessments are performed or myeloblast value is missing, blast value from peripheral blood is missing or $\leq 2\%$, and extramedullary leukemia is missing or not done, the response will be classified as NE. In any case response cannot be categorized as CR, CRp, CRi, PR or NE, it will be categorized as NR.

Relapse:

Relapse after CR, CRh, CRp or CRi is defined as a reappearance of leukemic blasts in the peripheral blood ($>2\%$) or $\geq 5\%$ myeloblasts in the bone marrow not attributable to any other cause or reappearance or new appearance of extramedullary leukemia.

Relapse after PR is similarly defined with reappearance of significant numbers of peripheral blasts and an increase in the percentage of myeloblasts in the bone marrow to $> 25\%$ or $>2\%$ blast in peripheral blood not attributable to any other cause or reappearance or new appearance of extramedullary leukemia.

Best Response:

Best response is defined as the best measured response to treatment for all visits (in the order of CR, CRp, CRi, PR, NR and NE) post-baseline. Subjects who achieve the best responses of CR, CRp, CRi, or PR will be classified as responders. Subjects who do not achieve at least PR will be classified as non-responders.

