End of treatment (for any period) or at the end of Cycle 26 of the maintenance period	Date of judgment of discontinuation or Cycle 26 Day 28 of the maintenance period	Scheduled date + 7 days	If the scheduled tests at discontinuation have been performed after the final study drug administration, the tests do not have to be repeated even if they were performed before the date of judgment of discontinuation.

During the maintenance period, the bone marrow test will be performed whenever it is determined to be clinically necessary.

- Visit Windows for Plasma PK Assessment for ASP2215 and Cytarabine

Induction period			
Assessment timing	Scheduled date (Day 1: Cycle 1 Day 1 Start of treatment)	Acceptable time range	Remarks
Cycle 1 Day 1 pre-dose	Day 1	Scheduled date, within 30 minutes before dosing	Blood sampling for cytarabine
Cycle 1 Day 3 pre-dose	Day 3	Scheduled date, within 30 minutes before dosing	Blood sampling for cytarabine
Cycle 1 Day 4 pre-dose	Day 4	Scheduled date, within 30 minutes before dosing	Blood sampling for ASP2215
Cycle 1 Day 4 1 hour post-dose	Day 4	Scheduled date, scheduled time \pm 10 minutes	
Cycle 1 Day 4 2 hours post-dose	Day 4	Scheduled date, scheduled time \pm 10 minutes	
Cycle 1 Day 4 4 hours post-dose	Day 4	Scheduled date, scheduled time \pm 20 minutes	
Cycle 1 Day 4 6 hours post-dose	Day 4	Scheduled date, scheduled time \pm 20 minutes	
Cycle 1 Day 4 10 hours post-dose	Day 4	Scheduled date, scheduled time \pm 20 minutes	
Cycle 1 Day 4 24 hours post-dose	Day 5	Scheduled date, scheduled time \pm 60 minutes and prior to Day 5 dosing	
Cycle 1 Day 8 pre-dose	Day 8	Scheduled date, within 30 minutes before dosing	
Cycle 1 Day 11 pre-dose	Day 11	Scheduled date, within 30 minutes before dosing	Blood sampling for ASP2215
Cycle 1 Day 17 pre-dose	Day 17	Scheduled date – 1 day, within 30 minutes before dosing	
Cycle 1 Day 28	Day 28	Scheduled date \pm 7 days	

Consolidation period			
Assessment timing	Scheduled date (Day 1: Cycle 1 Day 1 Start of treatment)	Acceptable time range	Remarks
Cycle 1 Day 1 pre-dose	Day 1	Scheduled date, within 30 minutes before dosing	Blood sampling for ASP2215
Cycle 1 Day 1 1 hour post-dose	Day 1	Scheduled date, scheduled time \pm 10 minutes	
Cycle 1 Day 1 2 hours post-dose	Day 1	Scheduled date, scheduled time \pm 10 minutes	
Cycle 1 Day 1 4 hours post-dose	Day 1	Scheduled date, scheduled time \pm 20 minutes	
Cycle 1 Day 1 6 hours post-dose	Day 1	Scheduled date, scheduled time \pm 20 minutes	

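### The not-evaluable rule omits a documented absence of extramedullary leukemia and missing blood counts, so some visits without evidence of leukemia are labelled NR; only the NR/NE split is affected

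*SAP*

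**What the plan says.** SAP section 6.1.1 builds NE from three conditions joined by 'and':

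- Marrow: "In the situation where no bone marrow assessments are performed or myeloblast value is missing".
- Blood: "blast value from peripheral blood is missing or" at most 2%.
- Extramedullary disease: "extramedullary leukemia is missing or not done, the response will be classified as NE".

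The residual rule follows: "In any case response cannot be categorized as CR, CRp, CRi, PR or NE, it will be categorized as NR".

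The other categories all rest on a marrow result. For CR, "CR is defined as a morphologically leukemia-free state at the post-baseline visit", with myeloblasts below 5%, neutrophils of at least 1,000/mm³ and platelets of at least 100,000/mm³. CRp is CR apart from a low platelet count. CRi is CR apart from a neutrophil count below 1,000/mm³, whatever the platelets. PR starts from "If bone marrow myeloblasts between 5% and 25% and a decrease from baseline of at least 50% in the marrow myeloblasts".

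Best response takes the highest category over post-baseline visits, and NR ranks above NE. Both are non-responders. Section 7.4 commits to reporting "The number and percentage of subjects in each category", with swimmer's plots, for the Phase 2 primary variable, and to category summaries after each treatment therapy.

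**The concern.** The blood condition lets a clean measured result count towards NE. The extramedullary condition does not let a negative result do the same. An extra reassuring finding therefore moves a visit from not evaluable to no response, while leaving the examination out keeps it at NE. That asymmetry looks like a drafting slip.

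The residual rule also catches visits where marrow is available and in the remission range but a blood count is missing. NE is closed to them because the myeloblast value is present, and CR, CRp and CRi cannot be told apart, so they become NR.

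At stake is what the NR and NE rows of the response tables mean. A programmer who follows the text literally will put visits with no sign of leukemia in the same row as visits with persistent disease.

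**Working it through.** No figure in the plan has to be reproduced; the check is of the rule's logic.

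**Step 1: no myeloblast value.** CR, CRp, CRi and PR are then impossible, so each visit is NE or NR. Applying section 6.1.1 as written to 3 blood states × 4 extramedullary states = 12 combinations:

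| Peripheral blasts | Missing | Not done | Absent | Present |
|---|---|---|---|---|
| Missing | NE | NE | **NR** | NR |
| ≤2% | NE | NE | **NR** | NR |
| >2% | NR | NR | NR | NR |

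NE arises in 4 of 12 and NR in 8. The two cells in bold contain no evidence of disease. If the third condition also admitted an absent finding, those two would move: NE 4 + 2 = 6, NR 8 − 2 = 6. No cell enters or leaves a remission category.

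**Step 2: marrow myeloblasts <5%, blood blasts ≤2%, no Auer rods, no extramedullary leukemia, a count missing.**

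| Neutrophils (/mm³) | Platelets (/mm³) | What the missing value could give | Category as written |
|---|---|---|---|
| ≥1,000 | missing | CR or CRp | NR |
| missing | ≥100,000 | CR or CRi | NR |
| missing | <100,000 | CRp or CRi | NR |
| missing | missing | CR, CRp or CRi | NR |
| <1,000 | missing | CRi only | CRi (not affected) |

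In the first four rows every possible value gives some form of complete remission, yet the residual rule gives NR. The last row is sound, because CRi does not depend on platelets.

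**Step 3: when best response moves.** As written, any visit with a myeloblast value is classed CR, CRp, CRi, PR or NR, never NE. A no-myeloblast visit graded NR instead of NE therefore changes best response only if no visit in that period has a myeloblast value. That means either that every marrow sample in the period lacks the value, or that there is no marrow in the period at all, as can happen in a later one. For the missing-count case, the change needs a subject with no other visit in the period classed NR or better, typically one whose only marrow visit lacks the count.

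**Step 4: which endpoints move.** NR and NE are both non-responders (6.1.1). Unknown or missing response stays in the denominator as non-response (6.1.2, 6.1.3). EFS treatment failure is defined by not reaching CRc or by stopping for lack of efficacy without a previous response, not by the NR label. RFS and the durations start from an achieved remission or response, and OS ends at death. None uses the NR/NE split.

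**Step 5: size per subject.** Section 4.1.2 gives 70 subjects for power and 80 to be enrolled. 1/80 = 1.25 percentage points; 1/70 = 1.43 percentage points.

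**The case against.** The strongest reply is that the affected visits should be rare. Section 6.1.1 ties response assessment to days of marrow sampling. The Phase 2 FAS in section 5.1 requires at least one post-baseline marrow assessment, and section 7.4 bases interpretation on the FAS. This largely stands. It does not close the gap: the NE rule itself provides for visits with no marrow, a sampling day can yield no myeloblast value, and the FAS asks for one marrow assessment overall rather than one per period. The missing-count case arises on marrow days, so the sampling-day link does not help there. Section 7.8 also runs the Phase 2 primary-variable subgroups on the TTE-FAS, which drops the marrow requirement.

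It may also be said that the word missing, applied to extramedullary leukemia, could mean absent. The same sentence uses the word twice for missing data and here pairs it with not done, so that reading is strained. The text would need clarifying even if it were intended.

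A reader might infer that Phase 1 maintenance visits without marrow would routinely be graded NR, since "the bone marrow test will be performed whenever it is determined to be clinically necessary". The SAP does not support this. That sentence says when extra marrow tests are done, not that a response is derived at other visits, and section 7.11.5 schedules a marrow at Maintenance Cycle 1 Day 1.

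**Conclusion.** The rule is wrong as written in two specific situations, and no other part of the SAP corrects it. The consequence is limited to the NR/NE split in the best-response category tables and the swimmer's plots. Each affected subject moves 1.25 to 1.43 percentage points, assuming a denominator between 80 and 70. The SAP gives no basis for the number of such subjects; it is probably small. Severity is minor.

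Two stronger readings should be resisted. A reader might infer that the primary result is biased; it is not, because NR and NE both count as non-response in the same denominator. A reader might also infer that the tables would declare these subjects resistant to treatment. The SAP makes no such statement and uses NR as a residual category, so the fault is a misleading label rather than a false claim of resistance.

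**What to change.** In section 6.1.1, change the third NE condition so that it is met when extramedullary leukemia is missing, not done or absent. Add a second route to NE: marrow myeloblasts below 5% with no evidence of leukemia, where a missing neutrophil or platelet count prevents assignment of CR, CRp or CRi. Keep NR as the residual category for all other visits. A visit with neutrophils below 1,000/mm³ and only platelets missing should stay CRi, as the present definition already gives.

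The cost is one amended definition and one derivation rule. The NE percentage may rise slightly and the NR percentage fall by the same amount. The CR count, the other response rates and the time-to-event endpoints stay as they are.
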